## PRECAUTIONS OF USE

- Single use: Do not wash to maintain the performances of the medical device.
- Do not sterilize.
- Do not use in direct contact with a wound.
- In the event of arterial bypass, cardiac failure, peripheral neuropathy (for example in case of diabetes), infected peri-ulcer dermatitis or acute cellulitis (erysipelas), use the compression system after specialist referral and under close medical monitoring.
- In case of ABPI  $\geq 1.3$ , suspicion of media calcific sclerosis or history of revascularisation, an extensive vascular assessment is recommended before initiating the compression therapy.
- In case of infected leg ulcer, start treating infection in combination with compression therapy.
- The efficacy of **URGO K2/ URGO KTwo** (or **URGO K2/ URGO KTwo Latex Free**) has been tested and validated for the application of KTech and KPress (or KPress Latex Free) together.
- Follow the application method given below to achieve the recommended therapeutic pressure. The PresSure System has been specifically designed to guide the application of the bandages.
- This compression system should be worn continuously day and night until the next care at the discretion of the clinician.
- If experiencing discomfort, pain or skin reactions whilst wearing this product, patient should contact his/her healthcare professional.
- Any serious incident linked to the product must be reported to the manufacturer and the National Competent Authority.

## INSTRUCTIONS FOR USE

### Before applying the bandages

- If a wound is present, apply an appropriate dressing before applying KTech.
- Examine the shape of the leg and identify any areas at risk of excessive pressure (bony prominences). Protect and reshape leg with wadding if necessary.
- Measure the ankle circumference and choose the kit size accordingly (18-25 cm or 25-32 cm) (**Figure 1**). For ankle circumference  $> 32$  cm, the 25-32 cm kit may be used: the level of compression will approach the therapeutic pressure with the progressive oedema reduction.
- In the event of very stout legs, 2 kits may be used to cover the entire leg.
- It is preferable to apply the compression system first thing in the morning or after the patient's legs have been elevated for an hour to minimize any orthostatic oedema.
- Depending on the indication, assess the need for toe to knee or toe to thigh bandaging and choose the appropriate kit width according to the following application method.

### Application method

#### "Below – knee" application

1. Position the foot at 90° angle - "toes to nose" (**Figure 2**).
2. Ensure the wadding side of KTech is in contact with the skin, with the printed pressure indicators visible on the upper (towards the top of the leg) side (18-25 cm kit size) or at the middle (25-32 cm kit size) of the bandage. Start at the base of the toes, making one or two wraps around the foot to anchor the bandage with a moderate stretch, depending on vascular status, foot shape and presence of oedema (**Figure 3**).
3. Take the heel, making a figure eight wrap around the ankle. Ensure that the heel is fully covered to avoid frictions (**Figure 4**).
4. From the ankle, wrap up to the knee in spirals, stretching the bandage so that the pressure indicators form circles. To achieve correct overlap, cover pressure indicators (18-25 cm kit

size: 50% (1/2) overlap of the bandage width; 25-32 cm kit size: 2/3 overlap of the bandage width) **(Figure 5)**.

Finish 2 cm below popliteal space.

 Cut off with a pair of scissors any excess bandage as extra wrapping will increase the pressure **(Figure 6)**. Secure with tape.

5. Apply KPress (or KPress Latex Free) over KTech using the same application technique as KTech. For patient comfort, allow a small border of KTech at the toes and knee so that only KTech is in direct contact with the skin.

Once applied, press down gently on the bandage to ensure full cohesion **(Figure 7)**.

#### "Toe to thigh" application

If necessary, first bandage the toes using an appropriate bandage.

For full leg bandaging, use the same application technique as the "below-knee" application.

During the application, the knee should be slightly bent to ensure patient mobility.

Several KTech must be used to continue the application to the top of the thigh **(Figure I)**: when applying a new KTech, start by performing one turn around the previous KTech.

Cover the knee avoiding that the edge of KTech is positioned over the popliteal space to avoid skin lesions.

 Cut off with a pair of scissors any excess of KTech and secure with tape.

Apply KPress (or KPress Latex Free) over KTech using the same sequence of bandages and application technique as KTech **(Figure II)**. Once applied, press down gently on the bandage to ensure full cohesion and secure with tape if necessary.

	DO NOT RE-USE
	CAUTION
	CONSULT INSTRUCTIONS FOR USE
	BATCH CODE
	USE-BY DATE
	CATALOGUE NUMBER
	MANUFACTURER
	MEDICAL DEVICE
	COMPRESSION LEVEL
	KIT SIZE
	URGO K2/URGO KTwo: PRESENCE OF NATURAL RUBBER LATEX
	URGO K2 Latex Free/URGO KTwo Latex Free: NOT MADE WITH NATURAL RUBBER LATEX
	BANDAGE WIDTH

 Laboratoires URGO - [name]

## APPENDIX (ii)

### UrgoStart Plus / UrgoStart Plus Non Border

DRESSING WITH SOFT-ADHERENT TLC-NOSF HEALING MATRIX TO REDUCE HEALING TIME AND WITH POLY-ABSORBENT FIBRES TO CLEAN THE WOUND

#### **□ DESCRIPTION:**

**UrgoStart Plus** is an innovative, patented dressing developed by Laboratoires Urgo composed by two exclusive technologies, TLC-NOSF healing matrix and poly-absorbent fibres.

**UrgoStart Plus** is composed of:

- A soft-adherent TLC-NOSF matrix, composed of lipido-colloid particles, polymers and an exclusive component, NOSF (Nano-Oligo Saccharide factor) which reduces healing time. It is combined with polyacrylate poly-absorbent fibres, which guarantee wound cleaning (of slough, exudate, and bacterial residue)
- A super-absorbent layer
- A vapour permeable waterproof outer film.

This specific combination is a patented structure.

#### **PROPERTIES:**

**UrgoStart Plus** reduces healing time and cleans the wound of slough, exudate, and bacterial residue.

The TLC-NOSF healing matrix forms a gel when in contact with the wound and reduces healing time by inhibiting excess metallo-proteinases, which degrade the extracellular matrix. It also creates a moist environment and promotes the action of the key cells involved in the healing process (fibroblasts, keratinocytes, and macrophages).

When in contact with the wound, the poly-absorbent fibres in **Urgostart Plus** gel. The dressing absorbs and traps slough, exudate and bacterial residue present in the wound, for an autolytic desloughing. The poly-absorbent fibres offer a high level of cohesion of the dressing allowing it to be removed painlessly in one piece, without causing trauma to the wound.

The poly-absorbent pad and the super-absorbent layer in **UrgoStart Plus** ensure a high absorption and fluid management of exudate preventing maceration. The dressing can be used under compression bandage when prescribed.

**UrgoStart Plus** water proof backing is soft, very conformable and non-occlusive which allows the dressing to conform and adapt to each different wound. It also prevents fluid leakage and bacteria strikethrough. Its high vapour permeability characteristics allow the excess exudate to evaporate, preventing from the risk of maceration. The dressing can adapt to different body movements, ensuring patient comfort. Due to its transparency, it is possible to monitor fluid strikethrough enabling the dressing change to be performed only when needed.

**UrgoStart Plus** has multiple properties:

1) Healing properties:

- Reduction of healing time combined with cleaning of all materials present in the wound (slough, exudate, bacterial residue)
- Absorption of exudate
- Management of minor bleeding wounds
- Creation and maintenance of a moist wound environment that promotes healing
- Atraumatic removal
- Respect of peri-wound skin

2) Comfort and ease of use:

- Painless removal
- Very conformable and easy to position due to soft-adherence
- A vapour permeable waterproof outer film

The efficacy of TLC-NOSF on reduction of healing time has been demonstrated in randomised controlled clinical trials and in a pooled analysis of observational studies.

### **INDICATIONS:**

**UrgoStart Plus** is indicated for all stages (from the desloughing stage to complete healing) of exuding wounds, including chronic wounds (leg ulcers, pressure ulcers, diabetic foot ulcers) and long-standing acute wounds.

### **INSTRUCTIONS FOR USE:**

- Wound preparation:
  - Clean the wound as per local protocol and rinse the wound with normal saline.
  - If an antiseptic has previously been used, rinse the wound carefully with normal saline before applying **Urgostart Plus**.
  - Dry the surrounding skin carefully.
  - The use of **Urgostart Plus** does not dispense with the need for mechanical debridement if required.

- Dressing application:
  - Gently remove the protective tabs.
  - Apply the soft-adherent side of **UrgoStart Plus** directly to the wound.
  - Apply a suitable bandage or compression bandage system when prescribed.
- Dressing changes:
  - Remove the dressing when it becomes saturated and clean the wound if necessary.

It is recommended to change **UrgoStart Plus** every 1 to 2 days during the wound desloughing phase, then to adapt the renewal frequency according to the volume of exudate and the clinical progress of the wound. It can be left in place for up to 7 days.

Discard any unused parts of the dressing.

#### **WARNINGS AND PRECAUTIONS FOR USE:**

- The soft-adherent layer of **UrgoStart Plus** adheres to latex surgical gloves. Therefore, it is recommended that the tabs be used to facilitate application of the dressing.
- As it includes a super-absorbent layer, **UrgoStart Plus** should not be cut.
- If the wound shows signs of local infection, it is recommended that anti-microbial treatment (such as UrgoClean Ag) is used first before starting treatment with **UrgoStart Plus**.
- If an atypical ulcer presents induration or over-granulation, treatment with **UrgoStart Plus** should only be initiated after verifying that ulcer deterioration is absent, to prevent any delay in diagnosis.
- In the absence of clinical data regarding Epidermolysis Bullosa (even for longstanding lesions), the use of **UrgoStart Plus** is not recommended.
- Stinging or even painful sensations may be reported at the start of the treatment. These are usually linked to the healing process and the need to suspend treatment is rare.
- During desloughing, the wound may appear to get larger due to the gradual elimination of slough.
- Concomitant use with a cream, an ointment, an emulsion is not recommended.
- **UrgoStart Plus** must not be used in a hyperbaric chamber.
- Sterile individual packaging, for single use only: re-using a disposable dressing can lead to the risks of infection.
- Do not re-sterilise the dressing.
- (\*) Check that the sterile protector is intact before use. Do not use if package is damaged.

#### **CONTRA-INDICATIONS:**

- **UrgoStart Plus** facilitates the management of minor bleeding wounds. However, it should not be used for heavily bleeding wounds.
- In order not to delay any optimal treatment, **UrgoStart Plus** is contra-indicated in cancerous wounds and wounds which may reveal a deep abscess.
- Do not use when there is a known sensitivity to **UrgoStart Plus**.

**APPENDIX (iii)****UrgoStart Plus Border**

ADHESIVE DRESSING WITH SOFT-ADHERENT TLC-NOSF HEALING MATRIX TO REDUCE HEALING TIME AND WITH POLY-ABSORBENT FIBRES TO CLEAN THE WOUND

**DESCRIPTION**

**UrgoStart Plus Border** is an innovative, patented dressing developed by Laboratoires Urgo composed by two exclusive technologies, TLC-NOSF healing matrix and poly-absorbent fibres.

**UrgoStart Plus Border** is composed of:

- A soft-adherent TLC-NOSF matrix, composed of lipido-colloid particles, polymers and an exclusive component, NOSF (Nano-Oligo Saccharide factor) which reduces healing time. It is combined with polyacrylate poly-absorbent fibres, which guarantee wound cleaning (of slough, exudate, and bacterial residue),
- A super-absorbent layer,
- A vapour permeable waterproof outer film with silicone adhesive on the edges.

This specific combination is a patented structure.

**PROPERTIES**

**UrgoStart Plus Border** reduces healing time and cleans the wound of slough, exudate, and bacterial residue.

The TLC-NOSF healing matrix forms a gel when in contact with the wound and reduces healing time by inhibiting excess metallo-proteinases, which degrade the extracellular matrix. It also creates a moist environment and promotes the action of the key cells involved in the healing process (fibroblasts, keratinocytes, and macrophages).

When in contact with the wound, the poly-absorbent fibres in **UrgoStart Plus Border** gel. The dressing absorbs and traps slough, exudate and bacterial residue present in the wound, for an autolytic desloughing. The poly-absorbent fibres offer a high level of cohesion of the dressing allowing it to be removed painlessly in one piece, without causing trauma to the wound.

The poly-absorbent pad and the super-absorbent layer in **UrgoStart Plus Border** ensure a high absorption and fluid management of exudate preventing maceration. The dressing can be used under compression bandage when prescribed.

**UrgoStart Plus Border** water proof backing is soft, very conformable and non-occlusive which allows the dressing to conform and adapt to each different wound. It also prevents fluid leakage and bacteria strikethrough. Its high vapour permeability characteristics allow the excess exudate to evaporate, preventing from the risk of maceration. The dressing can adapt to different body movements, ensuring patient comfort. The silicone adhesive borders guarantee that the dressing adheres well, can be easily repositioned and also well tolerated by the skin. The adhesive border prevents the need of a secondary dressing. Due to its transparency, it is possible to monitor fluid strikethrough enabling the dressing change to be performed only when needed.

**UrgoStart Plus Border** has multiple properties:

3) Healing properties:

- Reduction of healing time combined with cleaning of all materials present in the wound (slough, exudate, bacterial residue)
- Absorption of exudate
- Management of minor bleeding wounds
- Creation and maintenance of a moist wound environment that promotes healing
- Atraumatic removal
- Respect of peri-wound skin

## 4) Comfort and ease of use:

- Painless removal
- Very conformable and easy to reposition
- A vapour permeable waterproof outer film with silicone adhesive on the edges

The efficacy of TLC-NOSF on reduction of healing time has been demonstrated in double-blind, randomised, controlled clinical studies  and in a pooled analysis of observational studies .

 Edmonds M, et al. Sucrose octasulfate dressing versus control dressing in patients with neuroischaemic diabetic foot ulcers (Explorer): an international, multicentre, double-blind, randomised, controlled trial. *Lancet Diabetes Endocrinol.* 2018 Mar;6(3):186-196.

 Meaume S, et al. A randomized-controlled, double-blinded prospective trial with a TLC-NOSF wound dressing, in the local management of venous leg ulcers. *Wound Rep Reg.* 2012; 20(4):500-511.

 Meaume S, et al. Quality of life in patients with leg ulcers: results from CHALLENGE, a double-blind randomized controlled trial. *Journal of Wound Care.* 2017; 26 (7): 368-379.

 Münter KC, et al. The reality of routine practice: a pooled data analysis on chronic wounds treated with TLC-NOSF wound dressings. *J Wound Care.* 2017 Feb; 26 (Sup2): S4-S15. Erratum in: *J Wound Care.* 2017 Mar 2; 26(3): 153

## **INDICATIONS**

**UrgoStart Plus Border** is indicated for all stages (from the desloughing stage to complete healing) of exuding wounds, including chronic wounds (leg ulcers, pressure ulcers, diabetic foot ulcers) and long standing acute wounds.

The Sacral format is recommended for wounds in the sacrum region (pressure ulcers....).

## **INSTRUCTIONS FOR USE**

### **Wound preparation:**

- Clean the wound as per local protocol and rinse the wound with normal saline.
- If an antiseptic has previously been used, rinse the wound carefully with normal saline before applying **UrgoStart Plus Border**.
- Dry the surrounding skin carefully.
- The use of **UrgoStart Plus Border** does not dispense with the need for mechanical debridement if required.

### **Dressing application:**

- Gently remove the protective tabs.
- Apply the soft-adherent side of **UrgoStart Plus Border** directly to the wound (the adhesive silicone border should be at least 1 cm away from the wound).
- Smooth the dressing.
- Apply a compression bandage system when prescribed.

### **Application of the sacral version:**

- Place the dressing with the tip facing the sacral area.

### **Removal of the dressing:**

- Press down on the healthy skin, lift on the corner of the dressing and remove it carefully.

### **Dressing changes:**

- Remove the dressing when it becomes saturated and clean the wound if necessary.

It is recommended to change **UrgoStart Plus Border** every 1 to 2 days during the wound desloughing phase, then to adapt the renewal frequency according to the volume of exudate and the clinical progress of the wound. It can be left in place for up to 7 days. Discard any unused parts of the dressing.

**WARNINGS AND PRECAUTIONS FOR USE**

- As the **UrgoStart Plus Border** includes a super-absorbent layer, the central pad should not be cut. However, the adhesive edges can be cut if necessary, using sterile scissors to fit different wound or body shapes.
- If the wound shows signs of local infection, it is recommended that anti-microbial treatment such as UrgoClean Ag is used first before starting treatment with **UrgoStart Plus Border**.
- If an atypical ulcer presents induration or over-granulation, treatment with **UrgoStart Plus Border** should only be initiated after verifying that ulcer deterioration is absent, to prevent any delay in diagnosis.
- Regarding Epidermolysis Bullosa (even for longstanding lesions), the use of **UrgoStart Plus Border** is not recommended.
- Stinging or even painful sensations may be reported at the start of the treatment. These are usually linked to the healing process and the need to suspend treatment is rare.
- During desloughing, the wound may appear to get larger due to the gradual elimination of slough.
- Any excess hair should be removed to ensure the dressing has a good contact with the wound.
- In case of concomitant use with a cream, an ointment, an emulsion, let the skin dry out before applying the dressing.
- **UrgoStart Plus Border** must not be used in a hyperbaric chamber.
- Sterile individual packaging, for single use only: re-using a disposable dressing can lead to the risks of infection.
- Do not re-sterilise the dressing.
- (\*) Check that the sterile protector is intact before use. Do not use if package is damaged.

**CONTRA-INDICATIONS**

- **UrgoStart Plus Border** facilitates the management of minor bleeding wounds. However, it should not be used for heavily bleeding wounds.
- In order not to delay any optimal treatment, **UrgoStart Plus Border** is contra-indicated in cancerous wounds and wounds which may reveal a deep abscess.
- Do not use when there is a known sensitivity to **UrgoStart Plus Border**.

**APPENDIX (iv)****PARTICIPANT INFORMATION SHEET****Evaluation of the safety and effectiveness of the global treatment including multilayer compression therapy (Urgo KTwo®) in addition to an interactive dressing (UrgoStart® Plus) in the management of venous leg ulcers**

PROTOCOL NUMBER: EUS23-4

IRAS ID: 327680

PROJECT REF NO: 23/003/GHT

Patient Name: \_\_\_\_\_

**APPENDIX (vi)**

**LETTER TO THE COMMUNITY HEALTH CARE PROFESSIONAL**

Patient Identification Number for this trial:

**Evaluation of the safety and effectiveness of the global treatment including multilayer compression therapy (Urgo KTwo®) in addition to an interactive dressing (UrgoStart® Plus in the management of venous leg ulcers**

**PROTOCOL NUMBER: EUS23-4                      IRAS ID: 327680                      PROJECT REF NO: 23/003/GHT**

Practice Nurse / Community Nurse  
Email: (insert)

Dear Colleague,

Your patient, ..... has been seen by us for the management of his/her venous leg ulcer. As part of a clinical trial protocol, we have invited him/her to participate in a prospective, monocentre clinical trial, which has received a favourable opinion from the South West - Cornwall & Plymouth Research Ethics Committee.

This study evaluates the efficacy and tolerance of a specific procedure composed of a high compression system (Urgo K2) and an interactive wound dressing (UrgoStart Plus) for the local treatment of venous leg ulcers. After informing the patient of the nature of this study and how this study will be conducted and, after obtaining their written informed consent in accordance with Good Clinical Practice, the patient has agreed to participate in the study.

Thus, his/her ulcer should be treated locally with the UrgoStart Plus Pad, in combination with the Urgo K2 multilayer compression system. The treatment period is 12 weeks during which five clinical evaluations are scheduled by our team; at the initial visit (Day 0) and at the follow-up visits Week 2/ Week 4/Week 8 and Week 12.

Therefore, in between clinical assessments, we would appreciate it if you would carry out the care of the patient's ulcer according to the protocol that we have initiated and according to the instructions for use of the compression system given to him/her and the UrgoStart Plus Pad, used as a primary dressing.

In accordance with the protocol of this study, any modification or discontinuation of the trial treatment must be initiated by the investigating centre and any serious adverse event

(hospitalization, life-threatening event...) occurring during the study should be documented by our investigating centre.

Thus, we would also be grateful if you could inform us as soon as possible of any event relating to the treated lesion which you feel may compromise the follow-up of the treatment.

This clinical study does not involve any foreseeable risk for your patient, the expected benefit is an improvement in the condition of his/her ulcer which will result in a reduction of the surface area of the ulcer or even in its complete closure, and in a shorter period of time.

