### 2.2. SECONDARY OUTCOMES

The secondary criteria are to determine the following:

- Time to reach complete wound closure,
- Relative (and absolute) wound surface area reduction ( $\text{area}_{t0} - \text{area}_{t\text{last}}$ ),
- Percentage of patients with a  $\geq 30\%$  wound area reduction  $[(\text{area}_{t0} - \text{area}_{t\text{last}}) / \text{area}_{t0} \times 100]$  at Week 4 (18,19).
- Evolution of the ankle circumference,
- Patient Quality of Life through a specific the WoundQuol Questionnaire,
- The safety of the tested procedure (compression therapy system and dressings) through the nature and number of emergent local adverse events (i.e., events not present at baseline),
- Patients' acceptability of the procedure, evaluated by the investigator and by the patient,
- The change frequency per week over the treatment period.

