**Related to the leg ulcer:**

- Ulcer with ABPI<0.85,
- Ulcer which is clinically infected,
- Ulcer surface area partially or totally covered by black necrosis plaque,
- Malignant ulcer,
- Ulcer less than 3 cm, from any edge, to another wound located on the same limb.

**NB:** In the case of a patient presenting with several ulcers located on the same limb, the investigator must select at the inclusion visit only one wound for the evaluation (target ulcer), which best meets the selection criteria. This ulcer will be distant from the edge of any other wound on the same limb by a minimum of 3 cm. The other wound(s) will be treated with the investigator's usual treatment procedures for the primary wound dressing (*i.e.*, the compression system being the same for one entire lower limb).

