#### **1.2.5. Photographic record**

Photographs will be taken by the investigator at baseline and at every visit planned in the protocol till the end of the treatment period (Week 12 or before, if withdrawal or healing occurred), according to the investigator's normal procedures.

A ruler will be used when taking the photographic records.

At the end of this Inclusion visit, the investigator will give the Patient a letter for the nurse who will provide the care in the community, between two visits planned in the protocol. This letter will inform the community HCP about the study and will provide recommendations on how to use the products which are under evaluation.

The investigator, at the end of the inclusion visit, will give the patient an appointment for the next visit planned in the protocol, two weeks after the current one.

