### **12.2.1. Patient Information Sheet**

Every patient meeting the selection criteria must be informed by the investigator of the aims of the research, its methodology and its duration, the constraints and foreseeable risks, along with the benefits that he/she may reasonably expect from his/her participation.

The main points of the information provided to the patient must be included in the information document that the Investigator gives the patient before the start of the investigation.

The patient must know:

- that he/she may refuse to take part in the research,
- that he/she is able to withdraw from the study at any time without prejudice,
- that he/she will not have to bear any additional financial costs as a result of his/her participation in the investigation.

The investigator must answer any additional questions asked by the patient about the investigation at the time of selection and throughout the duration of the research.

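### The visible letter to the community nurse asks for fewer adverse events than the safety outcome counts, and says the study carries no foreseeable risk

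*Protocol*

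**What the plan says.** Section 5.2 (under Photographic record) has the investigator hand the patient a letter for "the nurse who will provide the care in the community, between two visits planned in the protocol". The letter is Protocol Appendix (vi). Its visible text does three things that matter here:

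- It asks the nurse to "inform us as soon as possible of any event relating to the treated lesion which you feel may compromise the follow-up of the treatment".
- It says that serious adverse events "should be documented by our investigating centre", and that any change to or stopping of the trial treatment must come from the centre.
- It states: "This clinical study does not involve any foreseeable risk for your patient".

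Section 2.2 lists as a secondary outcome "The safety of the tested procedure (compression therapy system and dressings) through the nature and number of emergent local adverse events". Section 7 sends local events of every grade of severity to the case report form. Sections 7 and 9 name the community professional, alongside the patient, as someone who telephones the principal investigator within 48 hours. This applies to local events that end treatment permanently and to serious events.

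**The concern.** The request in the letter passes through two filters. The event must concern the treated lesion, and the nurse must judge that it could compromise follow-up. The safety outcome has neither filter. Half of the tested procedure is a bandage that acts on much more skin than the ulcer, and many of its expected effects are mild and would not threaten follow-up.

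The risk sentence pulls in the same direction. A nurse who has been told that no risk can be foreseen has less reason to look for, or mention, a sore heel or a reddened shin.

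At stake is the completeness of the count of local adverse events. That count is a secondary outcome, and safety is part of the study objective stated in the Introduction.

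**Working it through.** The protocol gives no figure to reproduce. The check sets the texts side by side, with one small calculation on visit spacing.

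**Location.** The letter asks about the treated lesion. The note at the end of section 4.3 describes "the compression system being the same for one entire lower limb", and the below-knee method in Appendix (i) starts at the base of the toes and ends with "Finish 2 cm below popliteal space". Section 2.2 names the compression system within the safety outcome. Pressure damage over a bony prominence, or a skin reaction away from the ulcer, is therefore plausibly an event of the tested procedure. It does not relate to the treated lesion in any ordinary reading of the letter.

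**Severity.** The letter asks only for what the nurse thinks may compromise follow-up. Section 7 applies no severity threshold to local events. A mild or short-lived event that leaves follow-up intact is within section 7 and outside the request.

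**Risk sentence.** The letter denies foreseeable risk. The Precautions of use in Appendix (i) anticipate discomfort, pain or skin reactions under the bandage. The Warnings in Appendices (ii) and (iii) anticipate stinging or pain early in treatment. These effects are mostly minor, but they are foreseen, so the sentence is inaccurate as written.

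**How long an event could go unseen by the centre.** Nominal visits fall on Days 0, 14, 28, 56 and 84.

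- Gaps: 14 − 0 = 14, 28 − 14 = 14, 56 − 28 = 28 and 84 − 56 = 28 days. The longest nominal gap is 28 days.
- With the windows in sections 5.3 and 5.5, Week 4 on Day 26 followed by Week 8 on Day 58 gives 58 − 26 = 32 days. Week 8 on Day 54 followed by Week 12 on Day 86 gives 86 − 54 = 32 days.

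A transient event can begin and resolve within such a gap. The calculation assumes that the ulcer stays open to Week 12 and that neither nurse nor patient makes contact in between. It bounds the delay and says nothing about how many events are missed.

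**The case against.** The strongest reply is that the comparison uses the wrong standard. Sections 7 and 8 say what goes into the case report form, and the investigator completes that form. The reporting duties placed on the community professional are narrower: serious events, and local events that stop treatment for good. The letter touches both, because stopping must be initiated by the centre and serious events are to be documented there. The sentence that follows asks the nurse to inform the centre *also* of lesion events, which implies that serious events are passed on too. This stands: the letter does not breach a duty the protocol places on the nurse. What remains is practical. The investigator can record only what reaches the centre, and the nurse is often the first to see a problem between visits.

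The protocol also does not define *local*. A footnote in Appendix (ix) calls for a photograph of the treated ulcer when a local adverse event occurs, which fits a reading centred on the lesion. Counting limb-level events is therefore an inference, although naming the compression system in section 2.2 supports it.

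Three stronger readings are tempting and are not supported:

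- *The letter leaves out the 48-hour duties.* The part of the appendix after the last visible paragraph was removed from the copy reviewed, so nothing can be said about the whole letter.
- *The risk sentence contradicts section 12.2.1.* That section requires that patients be told "the constraints and foreseeable risks, along with the benefits that he/she may reasonably expect from his/her participation". It does not govern a letter to a nurse, and the patient sheet is not in the copy reviewed. The letter also directs the nurse to the instructions for use, where the effects are listed.
- *The nurse should report every intercurrent event.* Those events lie outside the section 2.2 safety outcome, and neither section 7 nor section 9 gives the nurse such a duty.

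**Conclusion.** The point holds in a limited form. The visible request is narrower in location and severity than the events the safety outcome is meant to count, and the risk sentence does not match the appended instructions. Mild, transient or off-lesion bandage events between visits are those most likely to be lost.

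A reader might infer a known under-count of adverse events. The documents do not support that: they give no event rate and no capture rate, so the size is unknown. The 28-day gap (32 with the windows) limits how long an event could wait for a visit if nobody called. It is not a measure of late or missing reports. Several safeguards remain. Local events are noted at each visit under section 5.3, lasting skin changes would be seen on examination, and patients may report for themselves.

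The conclusion assumes that bandage-related events on the limb count as local, and that the unseen end of the letter does not widen the request. The primary endpoint and its analysis are unaffected. Severity is minor, and the change is a cheap improvement.

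**What to change.** Reword the letter in Appendix (vi) as follows:

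1. Ask the nurse to tell the centre of any local adverse event on the bandaged limb, whatever its severity, and of any serious adverse event. Remove the condition about compromised follow-up.
2. If the unseen part of the letter does not already do so, restate the 48-hour telephone duty of sections 7 and 9 for serious events and for local events that lead to permanent discontinuation.
3. Replace the sentence on foreseeable risk with the effects named in the instructions for use: discomfort, pain, skin reactions and stinging.

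There is no need to ask nurses for every non-serious intercurrent event.

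The cost is a revised letter, notified to the ethics committee under section 12.1, and probably slightly more reporting by community nurses. No visit, procedure or analysis changes.
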